### **Statistical analysis plan:**

Category data will be presented in absolute and relative frequencies. Numerical data will be described by the arithmetic mean and standard deviation in the case of distributions following the normal, and in other cases by the median and limits of the interquartile range. Differences in category variables will be tested by the  $\chi^2$  test and, if necessary, the Fisher exact test. The normality of the distribution of numerical variables will be tested by the Shapiro-Wilk test. Differences of normally distributed numerical variables between two independent groups will be tested by Student's t test, and in case of deviation from normal distribution by Mann-Whitney U test, while in case of 3 or more groups will be tested by analysis of variance (ANOVA, PostHoc Bonferonni, Sheffe), and in case of deviation from the normal distribution by the Kruskal-Wallis test (PostHoc Conover). The correlation of continuous numerical variables will be evaluated by Pearson's correlation coefficient  $r$ , and in the case of ordinal distribution variables by Spearman's correlation coefficient  $\rho$  (rho). Differences in plasma concentrations of tramadol, O-demethyltramadol and N-demethyltramadol according to measurements (6 measurements) will be tested by analysis of variance for repeated measurements (normal distribution) or by Friedman test (Post-hoc Conover) in case of distributions that do not follow normal. The significance level will be set to Alpha = 0.05. MedCalc Statistical Software version 19.0.5 (MedCalc Software bvba, Ostend, Belgium; <https://www.medcalc.org>; 2019) and SPSS (version 16.0, SPSS Inc., Chicago, IL, USA) will be used for statistical analysis.

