## Background

Tramadol is a commonly used opioid analgesic for the treatment of moderate to severe acute and chronic pain. It is metabolized in the liver by O- and N-demethylation (phase I) and conjugation (phase II). O-demethylation of tramadol to the active metabolite O-demethyltramadol (ODT) is catalyzed by cytochrome CYP2D6, and N-demethylation to N-demethyltramadol (NDT) occurs via CYP2B6 and CYP3A4. The ODT metabolite of tramadol is an active metabolite that has 200-fold higher affinity for opioid receptors than tramadol itself and is thought to be responsible for the bulk of the analgesic effect of tramadol. CYP2D6 is a non-inducible enzyme, and its gene shows marked polymorphism due to which there are large individual and population differences in metabolism, analgesic action, and side effects of tramadol. Individuals carrying two inactive copies of CYP2D6 are poor metabolizers (PM) of tramadol compared to those carrying two copies of the extensive wild allele (EM). Individuals carrying one or more copies of inactive alleles or alleles of reduced CYP2D6 activity are intermediate metabolizers (IM), and those carrying more than two copies of wild alleles for CYP2D6 are ultrarapid metabolizers (UM). In addition to pharmacogenetics, the functional status of the liver and kidneys plays an important role in the pharmacokinetics of tramadol. Tramadol and the ODT metabolite are excreted by the kidneys, therefore renal failure, which is common in intensive care units (ICU), leads to the accumulation of tramadol and the ODT metabolite in the blood. More than 80% of tramadol is metabolized in the liver. There are known to be significant differences in the pharmacokinetics of tramadol between healthy subjects and patients with hepatic failure. In patients with hepatic failure, tramadol plasma concentrations are higher and the elimination half-life is longer. These changes are primarily due to decreased hepatic elimination. Patients in ICU often have mildly reduced liver function as part of multiorgan failure due to sepsis or Systemic Inflammatory Response Syndrome (SIRS), while major abdominal surgery and anaesthesia reduce liver perfusion and contribute to hypoxic liver damage. Drug distribution changes as a result of decreased protein production and changes in extracellular volume, and the activity and metabolic capacity of liver enzymes decreases resulting in increased concentration and decreased plasma elimination of drugs, which is often very difficult to predict. The CYP2D6 genotype-phenotype has been shown to be relatively effective in clinical practice, but it should be noted that a number of genotype-phenotype discrepancies have been documented, therefore the absorption, distribution, metabolism and excretion of tramadol cannot be determined by a single protein genotype. The expression and activity of CYP2D6 is regulated by a number of physiological, pathological and environmental factors. CYP2D6 expression is susceptible to changes in infection states or systemic inflammatory response associated with elevated cytokine values. Expression of CYP2D mRNA and protein is reduced by proinflammatory cytokines in the liver of mice and rats, while administration of anti-inflammatory cytokines such as IL-10 reduces CYP3A activity. This decrease was not observed for CYP2D. At low CYP2D6 activity or when O-demethylation of tramadol is reduced, tramadol is primarily metabolized by N-demethylation. A study in cancer patients known to have a chronic inflammatory condition accompanied by elevated values of proinflammatory mediators showed that elevated IL-6 values correlated with N-demethylation of tramadol and patient tolerance to the analgesic effect of tramadol. Surgical stress, anaesthesia, starvation, postoperative pain, emergency surgery, and surgery for malignant diseases contribute to the development of a systemic inflammatory response. Hypothermia or hyperthermia, leucocytosis or leukopenia, tachycardia and tachypnoea, are clinical components of SIRS which is often difficult to distinguish clinically from acute inflammation, but in both conditions

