
there is an increase in proinflammatory cytokines, CRP, and PCT. During the first 24 hours, SIRS is common and is not a good predictor of a patient's final outcome, but if the proinflammatory response lasts longer than 24 hours, then it is associated with higher mortality. In addition to elevated values of proinflammatory cytokines, CRP, and PCT, low cholinesterase values in elderly patients are a good indicator of a systemic inflammatory response due to infection, SIRS, and trauma and are an independent risk factor for poor hospital outcome. Decreased serum cholinesterase in the development of SIRS occurs before the rise in CRP, and it is a good marker of early detection of the systemic inflammatory response. Mild or subtle hepatic dysfunction is often seen in patients in intensive care units due to hepatocellular damage caused by hypoxemia due to decreased hepatic flow and degranulation of neutrophils into hepatic sinusoids in sepsis or SIRS. Therefore, the metabolism and analgesic effect of tramadol in ICU patients after major surgeries will depend on a number of factors. On the one hand of the polymorphism of the CYP2D6 gene, and on the other of the state of important organ systems involved in the metabolism and elimination of tramadol, as well as the development of a systemic inflammatory response that alters cytochrome activity.

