### **Objectives**

1. measure the plasma concentrations of tramadol, O-demethyltramadol and N-demethyltramadol in a patient admitted to the intensive care unit (ICU) after major abdominal surgery;
2. examine differences in tramadol, ODT and NDT concentrations with respect to CYP2D6 gene polymorphism;
3. examine the effect of systemic inflammation on the concentrations of tramadol, ODT and NDT in the early postoperative period;
4. examine the analgesic effect of tramadol with respect to systemic inflammation and organic dysfunction.

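### Objective 3 asks for the effect of systemic inflammation on tramadol, ODT and NDT, but every planned test is unadjusted, so differences in prior organ function or extent of surgery could be mixed into the answer

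*Combined protocol and SAP*

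**What the plan says.** The third item under Objectives is to "examine the effect of systemic inflammation on the concentrations of tramadol, ODT and NDT in the early postoperative period". The design section describes a prospective observational study, so inflammation status is not randomised.

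The statistical analysis plan gives these tools for numerical outcomes:

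- two groups: "Differences of normally distributed numerical variables between two independent groups will be tested by Student's t test", with Mann-Whitney if not normal;
- three or more groups: ANOVA or Kruskal-Wallis with post-hoc tests;
- "The correlation of continuous numerical variables will be evaluated by Pearson's correlation coefficient", or Spearman's coefficient;
- for the concentrations, differences "according to measurements (6 measurements) will be tested by analysis of variance for repeated measurements (normal distribution) or by Friedman test".

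It names no regression, covariate, stratified analysis or partial correlation. Nothing says whether the effect of inflammation includes the part that acts through renal and liver function.

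The Background says that metabolism depends on CYP2D6 genotype and also on "the state of important organ systems involved in the metabolism and elimination of tramadol, as well as the development of a systemic inflammatory response". Renal failure is said to accumulate tramadol and ODT, and hepatic failure to raise tramadol. Two routes to liver impairment are described. One is surgical: "major abdominal surgery and anaesthesia reduce liver perfusion and contribute to hypoxic liver damage". The other is inflammation itself, through "degranulation of neutrophils into hepatic sinusoids in sepsis or SIRS".

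Under Patients and methods, a fall in cholinesterase appears in the definition of organ dysfunction (at or below 20% of normal) and again, without a threshold, in the definition of systemic inflammatory response. The inflammatory response is dated only as perioperative.

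**The concern.** Inflamed and non-inflamed patients may differ in more than inflammation. The Background says of the inflammatory response: "Surgical stress, anaesthesia, starvation, postoperative pain, emergency surgery, and surgery for malignant diseases contribute to the development of a systemic inflammatory response". Surgery and anaesthesia are therefore named as contributors to both inflammation and liver damage. Patients with worse kidneys or livers before dosing would have higher tramadol whatever their inflammatory state. The exclusions deal with extreme CYP2D6 metabolisers and CYP2D6 inhibitors; none is stated for renal or hepatic dysfunction.

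At stake is how Objective 3 can be read. A difference found by the planned t test, or the absence of one, could partly reflect prior organ function or surgical extent. For tramadol, impaired liver function and reduced enzyme activity both push concentrations up. For ODT, renal accumulation pushes up while reduced CYP2D6 activity pushes down, so mixing could create or hide a difference. Overlapping definitions add to this: one low cholinesterase value may help place a patient in both categories.

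**Working it through.** The documents give no sample size, effect size, SD or prevalence, so there is no figure of the plan to reproduce. Of the inputs below, only alpha = 0.05, the six samples and five doses in 24 hours come from the documents. **Everything else is assumed**, to show what would have to be true for the point to matter.

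**1. Size of the mixing.** Let one organ marker raise log concentration by g, and let its prevalence differ by *gap* between inflamed and non-inflamed patients. Then

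unadjusted minus adjusted log effect = g × gap.

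| g | gap | distortion of the ratio |
|---|---|---|
| any | 0 | exp(0) = 1.00 |
| 0.4 | 0.20 | exp(0.08) = 1.08 |
| 0.4 | 0.40 | exp(0.16) = 1.17 |
| 0.6 | 0.40 | exp(0.24) = 1.27 |

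**2. Effect on the planned t test.** Suppose inflammation has no effect, and organ dysfunction, arising from other causes, shifts log concentration by d within-stratum SDs with prevalence p0 (non-inflamed) and p1 (inflamed). The apparent difference is d(p1 − p0), with SD √(1 + d²[p0(1 − p0) + p1(1 − p1)]/2). For d = 0.8, p0 = 0.2, p1 = 0.5: difference 0.24, SD 1.06, standardised 0.23. With 50 per group and two-sided alpha 0.05, the test is significant in about 20% of studies; in simulation it was 20.0% unadjusted and 5.6% with the marker in a linear model. Over d = 0.5 to 1.0 and p1 = 0.4 to 0.6, the unadjusted rate is about 5% to 21% at 20 per group and 7% to 45% at 50 per group. If inflammation itself caused the dysfunction, these are not false positives but part of its total effect.

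**3. Which adjustment deals with which path.** In both scenarios 15% of patients have kidney and 15% have liver dysfunction before dosing, inflammation adds 20 points of new dysfunction per organ among those still free of it, g = 0.4 per organ, and there is no direct effect. The true total log effect is 0.85 × 0.20 × (0.4 + 0.4) = 0.136, a ratio of 1.15.

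- *Prior dysfunction raises the chance of SIRS* (0.40, plus 0.20 per affected organ; new dysfunction 10% without SIRS). P(SIRS) = 0.40 + 0.20 × 0.30 = 0.46. Prior dysfunction of each organ is 0.15 × 0.63/0.46 = 20.5% with SIRS and 0.15 × 0.37/0.54 = 10.3% without. Any dysfunction is then 0.205 + 0.795 × 0.30 = 44.4% against 0.103 + 0.897 × 0.10 = 19.3%, a gap of 25.1 points. Unadjusted ratio: exp(0.8 × 0.251) = 1.22. Adjusting for pre-dose organ values returns about 1.15.
- *Extent of surgery drives both* (extensive in half; P(SIRS) 70% against 30%; 40 points more new liver dysfunction). Extensive surgery is then 40 points more common with SIRS. Unwanted part: 0.85 × 0.40 × 0.40 × 0.4 = 0.054. Unadjusted ratio: exp(0.136 + 0.054) = 1.21. Pre-dose organ values leave this essentially unchanged; adding surgical extent brings it back to about 1.15.

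These results follow from how the scenarios are built. They show which variables are needed for which path, not that a model will succeed in this cohort.

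**4. Change over time.** If inflammation lowers elimination, its effect accumulates over the doses. In a one-compartment sketch, let k = ln 2/half-life, with half-life 5 to 8 h and k reduced by 30%. The spacing of the five doses is not given; 24/5 = 4.8 h and 24/4 = 6 h were used. The tramadol ratio at 1 h is exp(0.3k) = 1.03 to 1.04. Before dose 5 it is Σexp(−0.7kjτ)/Σexp(−kjτ), j = 1 to 4, which is 1.30 (8 h, 4.8 h) to 1.54 (5 h, 6 h). One averaged ratio would hide this growth.

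**The case against.** The strongest reply has four parts.

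*The shared cause is common to everyone.* All included patients have a laparotomy with resection under sevoflurane, and laparoscopic cases are excluded. A cause present in every patient cannot confound a comparison between them. This stands: only variation in surgery (extent, emergency, malignancy) can matter, and the documents do not show that it differs between the groups.

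*The unadjusted contrast may be what is wanted.* A reader might infer that it can be read as neither a total nor a direct effect. The documents do not support that. With no imbalance there is no distortion, and if organ dysfunction lies purely on the path from inflammation, the unadjusted contrast is the total effect.

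*Adjustment can do harm or nothing.* Adjusting for postoperative organ dysfunction removes part of a total effect, and pre-dose values alone do not address the surgical path. Both stand and shape the fix.

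*Renal values may well be on record.* A reader might infer that urea and creatinine are never measured, because the measurement schedule does not name them. That goes too far: the schedule includes standard laboratory findings after induction and routine ones postoperatively, and renal dysfunction is defined through serum nitrogen metabolites.

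The ANOVA for three or more groups does not rescue the plan. No groups combining inflammation with organ function are named, and a one-way test would not by itself isolate inflammation.

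**Conclusion.** The point holds as a gap in the analysis that should be fixed. That no adjusted analysis is planned, and that the target effect is not stated, can be read directly from the text and is held with high confidence. The consequence is conditional: mixing arises if pre-dose organ function or surgical extent differs by inflammation status. Its size and direction cannot be taken from the documents, and zero is possible. The illustrative distortions of 1.00 to 1.27 rest wholly on assumed inputs and are not an estimate for this cohort. The cholinesterase overlap is real in the wording; how far it ties the two labels together depends on how the criteria are combined. Remaining EM/IM genotype differences are a source of noise and chance imbalance, not a shown confounder.

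**What to change.** 1. State that the main analysis of Objective 3 targets the total effect of inflammation (or its association), and state when the SIRS, renal and liver values are taken.
2. For each analyte, pre-specify one linear mixed model on log concentration with a random patient intercept, sampling time, SIRS, SIRS-by-time, EM/IM group, one named liver measure from the post-induction sample (for example bilirubin or GGT), one preoperative or post-induction renal measure if the standard laboratory findings include it, and the surgical factors on record (emergency, malignancy, extent). Report SIRS geometric mean ratios with 95% CIs, by time and averaged, as adjusted associations.
3. As a secondary analysis, repeat with postoperative renal and liver dysfunction added, labelled as the part not acting through organ function.
4. In these models, do not let cholinesterase count for both inflammation and liver dysfunction.
5. Keep repeated-measures ANOVA or Friedman as description for Objective 1.

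Cost: SAP wording and modest analysis work. Genotype and post-induction bilirubin and GGT are already planned; the sponsor must confirm that renal, postoperative liver and surgical data are recorded. The covariate list must stay short because the sample size is unstated. Residual confounding should be stated as a limitation, since post-induction values cannot capture organ damage arising during surgery.

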After induction under general anaesthesia, in addition to standard laboratory findings, plasma concentrations of albumin, cholinesterase, gamma-glutamyltransferase, bilirubin, C-reactive protein, procalcitonin will be measured, and pH, pO2, pCO2 and lactate values will be determined from an arterial blood sample. During the procedure, patients will be anesthetized by the method of general balanced inhalation anaesthesia with sevoflurane. Postoperatively, vital parameters, such as temperature, pressure, pulse and diuresis, will be continuously monitored in the ICU, and postoperative values of arterial blood gases, lactate and routine laboratory findings - complete blood count - will be determined. In the ICU patients will receive a total of 500 mg of tramadol intravenously divided into 5 doses during the first 24 hours of admission to ICU.

Plasma concentrations of tramadol, O-demethyltramadol and N-demethyltramadol will be measured 1, 2 and 4 hours after the first dose, and immediately before the 2nd, 3rd and 5th doses. In total, therefore, there will be 6 measurements within 24 hours. Determination of the concentration of tramadol and ODT and NDT metabolites from patient

plasma samples will be performed by high performance liquid chromatography (HPLC) on a Shimadzu Nexera XR (Shimadzu Corporation, Kyoto, Japan) on a reverse phase chromatographic system with fluorescence detection (excitation wavelength 200 a emission 301 nm). Separation will be performed on an Agilent Zorbax SB-C8 column, 3.5  $\mu$ m, 4.6x150 mm (Agilent Technologies, Santa Clara, CA, USA) using a mobile phase consisting of methanol and 1.5 mM H3PO4 in a ratio of 19:81), pH 2.5.

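### Tramadol, ODT and NDT are analysed only as separate, unadjusted concentrations, which cannot by themselves separate a CYP2D6 pathway change from dilution or slow excretion; pre-specified metabolite ratios should be added beside them.

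*Combined protocol and SAP*

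**What the plan says.** Under Objectives, Objective 2 is to "examine differences in tramadol, ODT and NDT concentrations with respect to CYP2D6 gene polymorphism" and Objective 3 is to "examine the effect of systemic inflammation on the concentrations of tramadol, ODT and NDT in the early postoperative period". Both are worded as concentrations.

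The Statistical analysis plan addresses the three analytes by name in one place: "Differences in plasma concentrations of tramadol, O-demethyltramadol and N-demethyltramadol according to measurements (6 measurements) will be tested" by repeated-measures ANOVA or the Friedman test. That is a within-patient comparison over time. The group comparisons that Objectives 2 and 3 need fall under the general wording, for example "Differences of normally distributed numerical variables between two independent groups will be tested by Student's t test", with Mann-Whitney, ANOVA or Kruskal-Wallis as alternatives. None of these tests adjusts for renal function, hepatic function or fluid status. No ODT/tramadol, NDT/tramadol or ODT/NDT ratio is defined anywhere.

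Patients and methods has all three analytes measured in the same plasma samples: "In total, therefore, there will be 6 measurements within 24 hours".

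The Background supplies the reasoning behind the objectives. On distribution it states: "Drug distribution changes as a result of decreased protein production and changes in extracellular volume". It says that renal failure, common in intensive care, makes tramadol and ODT accumulate. On pathway it states: "At low CYP2D6 activity or when O-demethylation of tramadol is reduced, tramadol is primarily metabolized by N-demethylation".

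**The concern.** The scientific rationale concerns a balance between two pathways, less O-demethylation and relatively more N-demethylation. That is a relative quantity. A single analyte's concentration reflects formation, distribution volume and elimination together, and the Background names the last two as things that change in these patients.

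A lower ODT in inflamed patients could therefore come from reduced CYP2D6 activity or from a larger volume. An unchanged ODT could hide reduced CYP2D6 activity if slow renal excretion offsets it. The planned tests contain nothing that helps a reader choose between these explanations. The question matters for any statement about metabolism drawn from Objectives 2 and 3.

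**Working it through.** The documents give no sample size, effect size, SD or between-analyte correlation, so there is no planned figure to reproduce. All numbers below illustrate direction and rough size on assumed inputs.

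**1. Can a non-enzymatic change mimic or hide a pathway change?**

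A one-compartment parent–metabolite model was used. Assumptions: five equal IV doses spaced 24/5 = 4.8 h apart (the protocol gives five doses in 24 h but no interval); tramadol rate constant 0.115/h, of which 20% is renal, 40% O-demethylation and 40% N-demethylation; each metabolite eliminated at 0.10/h, half of it renal. With V, f_r and f_o the volume, renal clearance and CYP2D6 activity relative to normal, the amounts follow:

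- tramadol: dT/dt = −0.115·(0.2·f_r + 0.4·f_o + 0.4)·T/V
- ODT: dO/dt = 0.115·0.4·f_o·T/V − 0.10·(0.5·f_r + 0.5)·O/V
- NDT: dN/dt = 0.115·0.4·T/V − 0.10·(0.5·f_r + 0.5)·N/V

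Concentration is amount divided by V. Results just before dose 5, relative to normal:

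| Scenario | Tramadol | ODT | NDT | ODT/tramadol | ODT/NDT |
|---|---|---|---|---|---|
| Volume +25%, enzymes unchanged | 0.99 | 0.83 | 0.83 | 0.84 | 1.00 |
| Renal clearance halved | 1.11 | 1.25 | 1.25 | 1.12 | 1.00 |
| CYP2D6 activity ×0.7 | 1.13 | 0.76 | 1.08 | 0.67 | 0.70 |
| Renal halved and CYP2D6 ×0.7 | 1.26 | 0.95 | 1.35 | 0.75 | 0.70 |

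Across all six samples, the larger volume gives ODT of 0.65–0.83, ODT/tramadol of 0.79–0.84 and ODT/NDT of 1.00. ODT alone therefore falls with no enzyme change (first row), and it nearly conceals a real 30% enzyme effect (last row).

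**2. How often would dilution alone give a significant ODT difference?**

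Assume a uniform 20% dilution, 30 patients per group and two-sided alpha 0.05 (the plan states 0.05 but not sidedness). The log difference is |ln 0.8| = 0.223, and power ≈ Φ(δ/(SD·√(2/n)) − 1.96).

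- Log-SD 0.6: 0.223/(0.6 × 0.258) − 1.96 = −0.52, giving 30%.
- Log-SD 0.4: 0.223/(0.4 × 0.258) − 1.96 = 0.20, giving 58%.

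This would be a true difference in concentration. It would be false only as evidence on CYP2D6.

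**3. How far do the ratios solve it?**

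- ODT/tramadol: before dose 5, the larger volume moves it to 0.84, almost the same as ODT itself (0.83). Halved renal clearance raises it by 12%. Sampling precedes steady state and ODT has its own renal excretion, so protection is limited.
- ODT/NDT: it stays at 1.00 in the first two rows because the model eliminates both metabolites identically. If NDT is less renally cleared (20% instead of 50%), halved renal clearance raises ODT/NDT by up to 10%. It also moves with N-demethylation: a 30% fall there with CYP2D6 unchanged would raise it to 1/0.7 = 1.43.

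**4. Does a ratio gain power?**

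With equal log-SDs and correlation ρ, SD(log ratio) = SD·√(2(1−ρ)). For ODT 30% lower, δ = |ln 0.7| = 0.357. With 30 per group and log-SD 0.6, ODT alone has 63% power.

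| ρ | Log(ODT/tramadol), tramadol unchanged | Log(ODT/tramadol), tramadol +10% |
|---|---|---|
| 0 | 37% | 54% |
| 0.3 | 49% | 69% |
| 0.5 | 63% | 83% |
| 0.7 | 84% | 97% |

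Break-even is ρ = 0.5 with tramadol unchanged. With tramadol up 10%, δ = |ln(0.7/1.1)| = 0.452 and break-even is 1 − (0.452/0.357)²/2 ≈ 0.20.

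A simulated genotype contrast used n = 15.7·(SD/difference)². Its assumptions were intermediate-metabolizer O-demethylation at 0.65 of extensive, 6 h half-lives, 30% of clearance to each metabolite and 10% assay error. With log-SDs of 0.2 for volume and 0.3 for clearances, before dose 5 it needs about 18 per group for ODT, 13 for ODT/tramadol and 24–26 for ODT/NDT. ODT/NDT needed more patients than ODT at that sample in four of five variance settings tried.

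**The case against.** The strongest reply is that the plan does what its objectives ask. Both speak of concentrations. If inflammation expands volume and lowers ODT, that is an effect on concentrations, and the Background lists volume among the causes. The end of the Background frames the question as multifactorial: genotype, organ state and inflammation. Absolute ODT also matters in its own right, because ODT is the active metabolite. This stands. Ratios should not displace the concentrations, and the analysis plan does not contradict the objectives.

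A second reply is that neither ratio is a clean measure of CYP2D6. This also stands, as step 3 of the working shows. The Background attributes N-demethylation to CYP2B6 and CYP3A4 and reports a cytokine that lowered CYP3A activity without the same fall for CYP2D, so ODT/NDT can move while CYP2D6 does not.

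Three stronger readings are tempting, and the documents support none of them:

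- A reader might infer that power is lost by not using ratios. The documents give no variances or correlations, and a ratio can gain or lose power.
- A reader might infer that the plan will report dilution as altered metabolism. Nothing in it says so; the risk lies in later interpretation.
- A reader might infer that ratios would settle the question. They narrow it.

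What remains unanswered is that the plan names non-enzymatic causes of concentration change, has a pathway rationale, and offers neither a relative measure nor an adjustment to help separate them.

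**Conclusion.** The point holds as a limit on interpretation. Separate, unadjusted concentrations answer Objectives 2 and 3 as worded, but they do not by themselves support a conclusion about CYP2D6 metabolism.

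On the assumed model, ODT can fall by 17–35% from a 25% larger volume alone. A 30% loss of CYP2D6 activity can shrink to a 5% fall in ODT when renal clearance is halved. Both sizes rest on assumed clearance shares, rate constants and dose spacing. That concentrations mix the causes follows from the Background itself.

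ODT/NDT and ODT/tramadol add information because they respond differently to these causes. Neither is sufficient alone. No claim about power is made in either direction. This is a worthwhile, low-cost addition; it does not invalidate the planned concentration analysis.

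**What to change.** In the Statistical analysis plan:

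- Define log(ODT/NDT) and log(ODT/tramadol) for each sample as additional measures for Objectives 2 and 3. Compare them between genotype groups and between inflammation groups beside, not in place of, the three concentrations.
- State that any conclusion about CYP2D6 metabolism will rest on the ratios and concentrations together.
- State the limits. ODT/tramadol still depends on distribution volume before steady state and on renal excretion of ODT. ODT/NDT also depends on CYP2B6 and CYP3A4 activity and on similar elimination of the two metabolites. Both are to be read with renal function.
- If precision is discussed, say that any gain depends on between-analyte variances and correlations that are not yet known.

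The cost is a short addition to the analysis plan. The ratios come from samples already assayed, so no blood, assay or patient is added. The downsides are a few more derived variables and tests, and that a ratio does not show absolute exposure, which is why the concentrations stay. The ratios should be fixed before the data are seen, because one chosen afterwards would be open to selection.

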The analgesic effect of tramadol will be measured in patients who are conscious on the NRS scale (0 - no pain, 10 - most severe pain) 30 minutes before and 30 minutes after tramadol administration. An NRS value of 3 or less will be considered adequate analgesia, and in case of inadequate analgesia, an additional analgesic will be used - morphine 2 mg. In patients with impaired consciousness, the analgesic effect of tramadol will be examined by the Behavioral Pain Scale (BPS) (3 - no pain, 12 - most severe pain) and the Critical Care Pain Observation Tool (CPOT). A BPS value of 5 or less will be considered adequate analgesia, as well as CPOT values less than 2. Consumption of additional analgesic will be recorded regularly. Nausea, vomiting, and newly developed respiratory depression will be reported within 24 hours. In all patients, they will record the total time of hospitalization in ZIM, hospitalization and the patient's outcome - death or survival until discharge from the hospital.

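### The only planned test across the six concentrations drops every patient with an incomplete set, and no rule covers incomplete sets

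*Combined protocol and SAP*

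**What the plan says.** Under Patients and methods, concentrations of tramadol and its two metabolites "will be measured 1, 2 and 4 hours after the first dose, and immediately before the 2nd, 3rd and 5th doses". The section concludes: "In total, therefore, there will be 6 measurements within 24 hours". The total tramadol amount is "divided into 5 doses during the first 24 hours of admission to ICU". Three of the six samples are therefore tied to doses, and a complete set needs a patient who is still on the schedule, and still being sampled, when the fifth dose is due.

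The Statistical analysis plan names one test across these occasions for each analyte: differences "will be tested by analysis of variance for repeated measurements (normal distribution) or by Friedman test". The software is MedCalc and "SPSS (version 16.0, SPSS Inc., Chicago, IL, USA) will be used for statistical analysis". No procedure or missing-value option is named.

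No section covers a missed sample, interrupted dosing, a patient who does not reach the fifth dose, or death or ICU discharge during the first 24 hours. No mixed model, imputation or sensitivity analysis is planned. The document states no sample size and no expected rate of missing samples.

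**The concern.** Repeated-measures ANOVA and the Friedman test treat each patient as a complete block. One gap removes the whole block, including samples that were taken and assayed correctly. In intensive care after laparotomy with resection, some incomplete series should be expected, and the sample that depends on the fifth dose is the most exposed.

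Two things are at stake. The first is precision, which is lost whatever the reason for the gap. The second is possible bias. The Background says that renal failure "leads to the accumulation of tramadol and the ODT metabolite in the blood" and that hepatic failure raises tramadol concentrations. If the same patients more often miss the later samples, the remaining complete series would not represent the patients who were enrolled, and the comparison of late with early samples would be distorted.

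**Working it through.** **1. The plan's own figure.** Three post-dose samples (1, 2 and 4 hours) plus three pre-dose samples (doses 2, 3 and 5) make 3 + 3 = 6. This agrees with the stated number.

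**2. What the tests do with a gap.** One value was removed from a made-up data set of 20 patients by 6 occasions (120 values). A standard repeated-measures ANOVA routine (Python statsmodels) refused to run because the data were unbalanced. The Friedman test with the missing value omitted gave a statistic of 1.316 and p = 0.933, identical to deleting that patient. The two packages named in the plan were not tested.

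**3. Cost in precision, losses independent.** Let q be the chance that a sample is missing (assumed, since the document gives none). The share of patients kept is (1 − q)^6. The share of collected samples discarded is [6(1 − q) − 6(1 − q)^6] / [6(1 − q)] = 1 − (1 − q)^5. The last column is 40 / (1 − q)^6, rounded up, where 40 is also an assumption.

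| q | Patients kept | Collected samples discarded | Enrolled for 40 complete |
|---|---|---|---|
| 2% | 88.6% | 9.6% | 46 |
| 5% | 73.5% | 22.6% | 55 |
| 10% | 53.1% | 41.0% | 76 |

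**4. Cost if only the last sample is lost.** If a share d of patients lacks only the pre-dose-5 sample, five valid samples per such patient are discarded out of an average of 6 − d collected: 5d / (6 − d). For d = 5%, 10% and 20% this gives 4.2%, 8.5% and 17.2%.

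**5. Possible bias if loss relates to severity.** This is a simulation of 400,000 patients in which every input is assumed:
- Geometric means over the six occasions are proportional to 400, 330, 260, 220, 300 and 380.
- On the log scale, the patient SD is 0.35 and the residual SD 0.2.
- One SD of severity adds 0.2 to log concentration at the first sample, rising to 0.5 at the last.
- Only the last sample is lost, with a log odds ratio of 0.7 or 1.4 per SD of severity.

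The true ratio of last to 1-hour sample is 0.949. The all-samples column uses a likelihood analysis with unrestricted covariance.

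| Loss | Log OR | Last sample, complete cases / truth | Last / 1-hour ratio, complete cases | Last sample, all samples / truth |
|---|---|---|---|---|
| 5% | 0.7 | 0.983 | 0.940 | 0.996 |
| 5% | 1.4 | 0.969 | 0.932 | 0.993 |
| 10% | 0.7 | 0.968 | 0.930 | 0.993 |
| 10% | 1.4 | 0.944 | 0.917 | 0.986 |
| 20% | 0.7 | 0.937 | 0.913 | 0.986 |
| 20% | 1.4 | 0.897 | 0.889 | 0.974 |

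At 10% loss the last-to-first ratio is too low by a factor of 0.930 / 0.949 = 0.980 to 0.917 / 0.949 = 0.966, or 2.0% to 3.4%. When loss is unrelated to severity, both analyses recover the truth (ratio 1.00).

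**The case against.** The strongest reply is that this is a small gap in a descriptive observational study. Several parts of it stand.

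- **Selective loss is not documented.** A reader might infer that the patients lost will be those with the highest exposure or the worst course. The Background links organ failure to concentration, not to missed samples. The plan also records "the patient's outcome - death or survival until discharge from the hospital", but that covers the whole hospital stay and says nothing about the 24-hour sampling window. Samples missed for logistic reasons would cost precision only.
- **Other analyses survive.** A reader might infer that an incomplete patient vanishes from every concentration analysis, that Objective 1 can describe only completers, or that contrasts by inflammation or organ function will shrink. The document does not support this. The planned means or medians, two-group and multi-group tests and correlations do not need six values if they are run at each time point.
- **Direction is not fixed.** If severity multiplied all six concentrations equally, selecting on it would leave ratios between times unchanged. Losses at both ends of the exposure range could cancel in the overall level. The bias in the working arises because severity was assumed to matter more at later samples.
- **A mixed model is not neutral.** No pre-dose-5 sample exists for a patient who has died or stopped. The model implicitly supplies an on-schedule value, so the plan must say what is being estimated. A single random patient effect would also force equal correlation between all occasions.

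These points limit the size and certainty of the bias. They leave untouched that the one across-time test discards valid samples, and that the plan neither says so nor offers an alternative.

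**Conclusion.** The point holds as a gap in the across-time analysis with a better method readily available. The loss of precision follows from the named tests. Its size depends on a missing-sample rate that the document does not give: 11%, 26% or 47% of patients dropped at an assumed 2%, 5% or 10% per sample.

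Bias is conditional. If loss of the last sample relates to severity, and severity acts increasingly over time, then at 10% loss complete cases understate the last geometric mean by 3.2% to 5.6%. Using all samples reduces that to 0.7% to 1.4%. At 5% loss the complete-case error is 1.7% to 3.1%. It would be wrong to report selective loss, or damage to the group comparisons, as established. The change is worth making because it is cheap, not because the study fails without it.

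**What to change.** In the Statistical analysis plan:

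1. Make the primary across-time analysis, for each analyte, a linear mixed model on log concentration with sampling occasion as a factor, using every available sample. Use a covariance structure not limited to equal correlation, for example unstructured, or random intercept and slope. An unstructured 6 × 6 matrix has 6 × 7 / 2 = 21 parameters and no sample size is stated, so name the fallback in advance.
2. State that values after tramadol is stopped or after death are not observed, and that estimates refer to patients while on the dosing schedule.
3. Report the number of missing samples and the reason for each, at each of the six times, by inflammation and organ-dysfunction group. Reasons should be recorded prospectively, as they may not be recoverable later.
4. Keep repeated-measures ANOVA or Friedman on complete cases as a sensitivity analysis, with the number of patients it uses.

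This needs no extra patient or blood sample, only revised wording, a field for the reason and slightly more analysis. The model assumes that data are missing at random given the observed samples, so loss that depends on unobserved concentrations is reduced in effect but not fully removed.
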